### Primary objective analysis

We will separately estimate the risk of the safety events of interest (i.e. angioedema [primary endpoint; ‘*narrow*’ and hypersensitivity reactions as part of ‘*hypersensitivity reactions*’ definition], hypotension [using both a ‘*narrow*’ and a ‘*broad*’ definition], hyperkalemia,

hepatotoxicity, renal impairment) as IRs, i.e. as the number of safety events of interest divided by person-time, along with 95% CIs in cohorts 1-2 (per database and pooled, using a meta-analytical approach [details will be provided in the SAP]):

1. Cohort 1: HF patients newly starting treatment with sacubitril/valsartan (regardless of prior use of ACEIs or ARBs)
2. Cohort 2: in the sub-population of HF patients newly starting treatment with sacubitril/valsartan without prior exposure to ACEIs or ARBs.

In addition, we will estimate IRs and cumulative incidence for angioedema at pre-defined time points (e.g. at Week 1, Week 4, Week 8, Week 26, and Week 52 after the index date) during use.

### Secondary objective analysis

We will estimate IRs with 95% CIs (for all safety events of interest) and cumulative incidences (for angioedema only) in cohort 3 and 4 (by database and pooled, using a meta-analytical approach (details will be provided in the SAP).

In addition, we will estimate IRs and cumulative incidences for angioedema at pre-defined time points (e.g. at Week 1, Week 4, Week 8, Week 26, and Week 52 after the index date) during use (equal to the primary analysis, above).

In a subset of patients from cohort 3 (mix of prevalent and incident ACEI users at index date), we will conduct a sensitivity analysis to calculate the IR considering various different prevalent ACEI exposure periods prior to the index date.

### Exploratory objective analyses

Adjusted relative risks for the primary safety event of interest (angioedema [*'narrow'* definition]) will be estimated for each database as HRs with 95% CIs using Cox regression models comparing:

- a. new users of sacubitril/valsartan who are treatment-naïve to ACEIs and ARBs (cohort 2) to new users of ACEIs who are treatment-naïve to ACEIs/ARBs (cohort 4)
- b. new users of sacubitril/valsartan regardless of prior ACEI/ARB use (cohort 1) to users of ACEIs who are treatment-naïve to ACEI/ARB use (cohort 4)
- c. new users of sacubitril/valsartan regardless of prior ACEI/ARB use (cohort 1) to users of ACEIs regardless of prior use of ACEIs/ARBs (cohort 3)

Comparative analyses will be conducted separately in each database; pooled estimates will be provided by using a meta-analytical approach (details to be provided in SAP).

### Confounding

To display differences in the cohorts we will create a propensity score (PS) of (pre-defined) covariates for cohort 2 versus cohort 4; cohort 1 versus cohort 3; and cohort 1 versus cohort 4.

For the exploratory analyses we will adjust for the PS to limit confounding or potential channeling by applying PSOW (propensity score overlap weighting) (Li et al. 2018, Li et al. 2019, Mao et al. 2018), as a confounder control in multivariable regression models will be limited by the relatively low number of safety events and matching on PS would likely cause

loss of sacubitril/valsartan users that cannot be matched in case overlap of propensity scores is limited. Details will be provided in the SAP.

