##### Amendment rationale

The first interim report of LCZ696B2014 submitted to PRAC in March 2018, including data through December 2016, identified a total of 250 initiators of sacubitril/valsartan (regardless of prior ACEI/ARB use) fulfilling the inclusion criteria [REDACTED]. In the second interim report, and as part of the ongoing feasibility analyses, ARS data from Italy were included to complement the original five databases [REDACTED]. The third [REDACTED] and fourth interim report [REDACTED] in addition to ARS, included GePaRD data. These two additional databases were considered crucial to reach the expected sample size of 24,000 patient-years (PYs) at the planned end of data collection (December 2021). In addition, based on the results from the feasibility analyses [REDACTED] these data were considered to be of sufficient quality by Novartis to be added to the original five databases. This was confirmed by PRAC in their response in March 2021. The addition of these two databases is the main rationale triggering this protocol amendment. Furthermore, divergent from the initial LCZ696B2014 protocol v00 [REDACTED] all analyses will be performed in collaboration between the principal investigator (PI), as scientific lead, and the PHARMO Institute for Drug Outcomes Research. [REDACTED]

Other (substantial) amendments or updates to the original LCZ696B2014 protocol version 00 [REDACTED] are detailed below in [Table 3-1](#).

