#### 7.1.1 Rationale for study design

To obtain a robust estimate of the incidence of angioedema – the primary safety event of interest – as well as of the other safety events (i.e. hypotension, hyperkalemia, hepatotoxicity, and renal impairment) in patients newly starting sacubitril/valsartan (incident users), an initial cohort of all sacubitril/valsartan initiators will be identified (regardless of prior exposure to ACEIs or ARBs) with patient accrual beginning at the specific launch date of sacubitril/valsartan (see [Table 7-1](#)) in those EU countries from which healthcare database information will be used for this study (see [Section 7.4](#) ‘Data sources’). In addition, an initial contemporaneous comparator cohort of ACEIs initiators will be identified. Data collection will end when the necessary sample size of 24,000 PYs is reached (see [Section 7.5](#) ‘Study size/power calculation’), but on 31 December 2021 at the latest (even when the target sample size is not reached).

A new user design ([Ray 2003](#), [Food and Drug Administration 2013](#), [Yoshida et al 2015](#)) is proposed to minimize the risk of a prevalent user bias and depletion of susceptibles. This is of particular importance for ACEIs users. Sacubitril/valsartan was newly introduced to the market and the cohort of users therefore automatically consists of new users. As indicated in the sacubitril/valsartan ‘Summary of Product Characteristics’ (SmPC), it is contraindicated for patients with a known history of angioedema related to previous ACEI or ARB therapy, or with hereditary or idiopathic angioedema. The combination of sacubitril/valsartan with an ACEI is contraindicated due to the increased risk of angioedema. Sacubitril/valsartan must not be initiated within 36 hours after taking the last dose of ACEI therapy.

Since the majority of sacubitril/valsartan users are expected to have been treated with an ACEI or ARB before starting sacubitril/valsartan, these patients will likely have a lower baseline risk of angioedema as susceptible patients have been depleted. ACEI initiators who are treatment

naïve to ACEIs and ARBs however, will likely have a higher baseline risk of angioedema since this population includes all patients who are susceptible to an angioedema event.

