### 7.2.3 Study period

The study period during which patients can enter the study population will start at the sacubitril/valsartan launch dates in the countries of interest (see launch dates in [Table 7-1](#) below) and will end on the 30th of April 2021 at the latest. The total study time frame (including the beginning of the minimal 365 days look-back period before cohort entry) will begin in December 2014 at the earliest. With a data extraction date in December 2021, the end of data availability will range from December 2019 (GePaRD) through April 2021 (ARS).

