### **7.2.5 Cohort start**

The date of the first recorded prescription (or pharmacy fill) for sacubitril/valsartan or ACEI in the study period will be defined as the cohort entry (= start of follow-up or ‘index date’). A minimal look-back period of 365 days is used to determine baseline characteristics.

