### 7.3.1.2 ACEI user cohorts

- ACEIs – users regardless of prior ACEI/ARB use (cohort 3)

[figure not shown]
This group includes all patients fulfilling the inclusion criteria ([Section 7.2.4](#)) and using ACEIs during the study period – regardless of prior exposure to ACEIs or ARBs. This cohort will be a mix of prevalent and incident ACEI users.

- ACEIs – without prior use of ACEI/ARB - treatment-naïve (cohort 4)

Cohort 4 is the subset of patients from cohort 3. It includes patients who did not use ACEIs/ARBs in the 365 days prior to index date. This sub-cohort corresponds to new ACEIs users - naïve to ACEIs/ARBs.

Note: Patients can be included in more than one cohort. Patients changing from ACEI to sacubitril/valsartan will be included in the corresponding ACEI cohort, as well as the sacubitril/valsartan cohort (only the first change will be considered). Patients changing from sacubitril/valsartan to an ACEI, however, will be censored. [Figure 7-2](#) illustrates cohort allocation and start of follow-up based on various exposure scenarios for sacubitril/valsartan and ACEI users.

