### 7.3.3 Patient characteristics/demographics

The following patient characteristics at the index date will be summarized:

- Age (continuous, categorical [18-44, 45-64, 65-74,  $\geq 75$  years, no reference needed])
- Sex (female as reference)
- Ethnicity (only available in CPRD, but recording rather incomplete [Mathur et al 2014](#))
- Comorbidities (i.e., diseases/conditions already prevalent before the index date, using entire available history in patients' electronic medical records (yes/no [no = reference])), i.e.
  - Hypertension
  - Myocardial infarction
  - Stroke or transient ischemic attack (TIA)
  - Angina pectoris
  - Atrial fibrillation
  - Valvular disease
  - Diabetes mellitus
  - Respiratory disease (asthma, chronic obstructive pulmonary disease [COPD])
  - Allergic reactions (e.g., to food, seasonal allergies, drug rash, urticaria)
  - Moderate to severe chronic kidney disease (CKD), will not be presented for the respective cohorts examining sacubitril/valsartan or ACEI use and the risk of renal impairment (exclusion criterion)
  - Chronic hepatic disease, will not be presented for the respective cohorts examining sacubitril/valsartan or ACEI use and the risk of hepatotoxicity (exclusion criterion)

- 
- Comedication ((yes/no [no = reference]) to characterize patients in the respective cohorts (based on prescription/dispensing at index date or within 365 days prior to index date):
    - ACEIs (assessed excluding index date)
    - ARBs (assessed excluding index date)
    - Other renin angiotensin aldosterone system (RAAS) targeting drugs (e.g. aliskiren)
    - Beta-blockers
    - Calcium channel blockers
    - Mineralocorticoid receptor antagonists (MRAs)
    - Loop diuretics
    - Other diuretics (thiazides, potassium-sparing diuretics [excluding MRAs and loop diuretics])
    - Digoxin
    - Ivabradine
    - Nitrates
    - Hydralazine
    - Antiarrhythmic agents
    - Anticoagulants
    - Antiplatelets (including prescription aspirin)
    - Lipid lowering drugs (excluding statins)
    - Statins
    - Antidiabetics
    - Fluoroquinolones
    - Non-steroidal anti-inflammatory drugs (NSAIDs)

To approximate heart failure severity and overall health status of the patient, the use of the following will be evaluated:

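### In exploratory comparison c (cohort 1 versus cohort 3), ongoing ACEI users are indexed near launch and sacubitril/valsartan starts come later, with no calendar-time variable among the listed covariates

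*Protocol*

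**What the plan says.** Three rules in the protocol meet here.

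- **Entry.** Section 7.2.5: the "first recorded prescription (or pharmacy fill) for sacubitril/valsartan or ACEI in the study period will be defined as the cohort entry". Section 7.2.3: the period "will start at the sacubitril/valsartan launch dates in the countries of interest".
- **Cohort 3.** Section 7.3.1.2: "This cohort will be a mix of prevalent and incident ACEI users". Cohort 4 is the subset with no ACEI or ARB in the 365 days before index.
- **Covariates.** Section 7.3.3 opens with "The following patient characteristics at the index date will be summarized". It lists age, sex, ethnicity (CPRD only), comorbidities, comedication and a count of heart failure drugs, and later refers to these as covariates. The Variables paragraph of the abstract names demographics and other patient characteristics, comorbidities and concomitant medications as potential confounders. Neither place names index year or calendar period.

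The Confounding part of section 7.7.1.2.2 says "we will create a propensity score (PS) of (pre-defined) covariates for cohort 2 versus cohort 4", and in the same sentence for cohort 1 versus 3 and cohort 1 versus 4. Overlap weighting is then applied, with details left to the SAP. Comparison c, cohort 1 versus cohort 3, is the third exploratory objective.

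**The concern.** A patient already on an ACEI at launch enters cohort 3 at the next refill, so the ongoing users bunch at the start of the study period. Sacubitril/valsartan starts cannot bunch there. The first interim report, with data through December 2016, found 250 of them (section 3), and in Italy reimbursement came 11 months after launch (Table 7-1). Patients who switch reinforce the ordering: they contribute ACEI time first, are censored at the switch (section 7.2.6), and then enter cohort 1 (section 7.3.1.2).

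Overlap weighting balances only what is in the score. If the score holds only what section 7.3.3 lists, comparison c sets later calendar time on sacubitril/valsartan against earlier calendar time on ACEI. Any change over the window in coding, capture or background therapy then passes into the hazard ratio. Pooling across databases would not remove a bias that runs the same way in each.

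The protocol accepts elsewhere that calendar time matters. It censors the primary analysis at 31 December 2019 because of COVID-19, and section 7.6.2 allows that coding may change. Yet the limitation that section 7.9 gives for prevalent ACEI users is depletion of susceptibles, not calendar time.

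**Working it through.** The plan gives no figure on calendar time to reproduce. The check has two parts.

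**1. Share of cohort 3 that could be indexed near launch.** Fourth interim figures, with ARS and GePaRD: cohort 3 almost 567,000 (section 7.1.2), cohort 4 116,041 (section 7.1.1).

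- Non-naïve share = 1 - 116,041/567,000 = 79.5%.
- Without ARS and GePaRD: 1 - 21,500/89,000 = 75.8%.

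This is an upper bound for ongoing ACEI users. It also counts prior ARB users, who may start an ACEI at any time, and ACEI users restarting within 365 days. The protocol gives no split.

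**2. How far a time trend would move the rate ratio.** From the documents: windows ending 31 December 2019 of 4.0 years (GePaRD, launch January 2016) and 3.75 years (Italy, launch April 2016), and the 11-month reimbursement lag in Italy.

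Assumed:

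- 79.5% of cohort 3 enters evenly over the first three months and the rest evenly over the window.
- Cohort 4 enters evenly over the window.
- Sacubitril/valsartan entry rises linearly from launch (from reimbursement in Italy).
- Time on treatment is exponential with mean 0.83 years (24,000 PY/29,000 patients), 2 or 4 years.
- There is no true treatment effect.
- The recorded rate changes by a constant percentage a year.

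Mean index time after launch in the 4-year window is 0.51 years for cohort 3, 2.00 for cohort 4 and 2.67 for sacubitril/valsartan. What drives the bias is when person-time falls:

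| Window, mean time on treatment | Mean calendar time of person-time, cohort 3 / sac/val (years) | Spurious ratio vs cohort 3, trend -5% / +5% | Trend -10% / +10% |
|---|---|---|---|
| 4.0 y, 0.83 y | 1.16 / 2.84 | 0.917 / 1.085 | 0.837 / 1.173 |
| 4.0 y, 2 y | 1.62 / 2.92 | 0.935 / 1.065 | 0.870 / 1.129 |
| 4.0 y, 4 y | 1.86 / 2.95 | 0.945 / 1.054 | 0.888 / 1.107 |
| 3.75 y, 0.83 y | 1.12 / 2.95 | 0.910 / 1.093 | 0.823 / 1.188 |
| 3.75 y, 2 y | 1.55 / 3.00 | 0.928 / 1.072 | 0.855 / 1.144 |
| 3.75 y, 4 y | 1.76 / 3.02 | 0.937 / 1.062 | 0.873 / 1.123 |

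Hand check of the first row: the gap is 2.84 - 1.16 = 1.68 years, and 1.05^1.68 = 1.085.

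Against cohort 4 the same model gives 0.960-0.980 or 1.019-1.038 at 5% a year, and 0.919-0.958 or 1.037-1.074 at 10%. In this model cohort 4 has the entry pattern that cohort 3 would have with no launch clustering. If fewer than 79.5% are indexed near launch, the cohort 3 figures move towards these.

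**The case against.** The strongest reply is that the content of a propensity score commonly belongs in the SAP. The Confounding paragraph calls the covariates pre-defined without listing them and defers to the SAP, and section 7.3.3 is introduced as a list to be summarised. That stands: one can say that calendar time is absent from the covariates this protocol lists, not that it is absent from the score. It does not dispose of the point, because the entry rule is fixed here. A SAP that added index year for comparison c without changing the index date would find little overlap.

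Several stronger readings are tempting and are not supported:

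- *Both ACEI cohorts bunch at launch.* Cohort 4 excludes anyone with ACEI or ARB use in the prior 365 days, so it holds no ongoing users. Any imbalance there comes only from rising uptake.
- *The protocol wrongly calls cohort 3 contemporaneous.* Section 7.1.1 says "an initial contemporaneous comparator cohort of ACEIs initiators will be identified". The word is used of initiators, as against a historical cohort.
- *A two-year index gap at 5% a year shifts the ratio by 10%.* That treats a gap in index dates as a gap in person-time. Cohort 3 is followed into later years, which shrinks the effect.
- *The 250 early starts describe the whole study.* They come from the five original databases. GePaRD later supplied 4,724 of 5,185 initiators in the feasibility work, and its early uptake is not given.

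The feasibility work found no major differences in the characteristics of ACEI users before and after launch. That is reassuring on case mix, but it does not test angioedema recording within the study window. Figure 7-1 plots general-population angioedema rates over time but is not visible, so no drift can be asserted or ruled out. Section 6.3 labels all comparisons exploratory, section 7.1.1 prefers cohort 2 versus 4, and section 7.9 already warns of bias in the comparison with prevalent users. Sampling error is likely to be larger than this bias: the interim cohort 1 rate of 0.7 per 1,000 PY has an interval of 0.4-1.1, about 1.6-fold or more either way (1.1/0.7 = 1.57; 0.7/0.4 = 1.75).

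**Conclusion.** The point holds for comparison c. As written, the entry rule places the ongoing ACEI users in cohort 3 near launch, sacubitril/valsartan starts come later, and the listed covariates cannot correct the difference. At most 79.5% of cohort 3 is affected. With no true effect, an assumed trend of 5% a year gives a spurious rate ratio of about 0.91-0.95 or 1.05-1.09, and 10% a year gives about 0.82-0.89 or 1.11-1.19. For the two comparisons with cohort 4, the corresponding shift is about 2-4% at 5% a year.

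These sizes rest on assumed entry patterns, treatment durations and trends. The documents show a route for bias, not a drift or its direction. This is a worthwhile, inexpensive improvement to one exploratory analysis; it does not touch the primary or secondary incidence rates.

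**What to change.** - For comparison c, replace the first-fill index for ACEI users with a fill sampled in the same calendar quarter as the sacubitril/valsartan starts, with eligibility and baseline covariates assessed at that fill. Secondary objective 2 can keep the present rule.
- Alternatively, stratify the Cox model by calendar period. This is simpler but weaker: the later strata would hold relatively few ongoing ACEI users, so the contrast would lean towards cohort 1 versus 4.
- Add calendar period of index to section 7.3.3, so that it also enters the score for cohort 2 versus 4 and cohort 1 versus 4.
- Report the index-year distribution for each cohort and database.

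Index date is already held, so no new data are needed. The cost is a re-indexing step in the shared SAS program and its R counterpart at ARS. The main risk is adding calendar time to cohort 1 versus 3 without re-indexing, which would leave poor overlap and put most of the weight on a small part of cohort 3.

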#### 7.7.1.2.3 Sensitivity analyses

Details on sensitivity analyses will be specified in the SAP, including potential safety event misclassification, potential COVID-19 impact, and the impact of duration of prevalent ACEI use in a subset of cohort 3. In the (ongoing) validation study, the proportion of true angioedema cases among the hypersensitivity reactions is calculated as the false negative rate (FNR). The FNR will be used to estimate what proportion of angioedema events might have been missed with the narrow definition of angioedema.

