## List of abbreviations

---

ACE(I)	Angiotensin Converting Enzyme (Inhibitor)
ADM	Administrative
AE	Adverse Event
ARB	Angiotensin Receptor Blocker
ARNI	Angiotensin Receptor Neprilysin Inhibitor
ARS	Agenzia Regionale di Sanità della Toscana
ATC	Anatomical Therapeutic Chemical
BIPS	Leibniz Institute for Prevention Research and Epidemiology – BIPS (formerly Bremer Institut für Präventionsforschung und Sozialmedizin)
BMI	Body Mass Index
BNF	British National Formulary
CHMP	Committee for Medicinal Products for Human Use
CI	Confidence Interval
CKD	Chronic Kidney Disease
COPD	Chronic Obstructive Pulmonary Disease
COVID-19	Corona Virus Disease – 2019
CPRD	Clinical Practice Research Datalink
CRO	Contract Research Organization
Db	Database
DE	Germany
DK	Denmark
EMA	European Medicines Agency
EMR	Electronic Medical Record
ENCePP	European Network of Centres for Pharmacoepidemiology and Pharmacovigilance
ES	Spain
EU	European Union
FNR	False negative rate
GePaRD	German Pharmacoepidemiological Research Database
GM	German Modification
GP	General Practitioner
GPP	Good Pharmacoepidemiology Practices
HES	Hospital Episode Statistics
HF	Heart Failure
HFrEF	Heart Failure with Reduced Ejection Fraction
HIV	Human Immunodeficiency Virus
HR	Hazard Ratio
HSD	Health Search Database
ICD-9	The International Classification of Diseases, 9 th Revision
ICD-10	The International Classification of Diseases, 10 th Revision
ICPC	International Classification of Primary Care
IQR	Interquartile Range
IR	Incidence Rate
IT	Italy

---

---

LBQ657	The active metabolite of the prodrug sacubitril
LCZ696	Sacubitril/valsartan
MRA	Mineralocorticoid Receptor Antagonist
NEP	Neutral Endopeptidase
NHS	National Health Service
NIS	Non-Interventional Study
NL	The Netherlands
NLP	Natural Language Processing
NSAID	Non-Steroid Anti-Inflammatory Drug
NYHA	New York Heart Classification
OTC	Over the Counter
PSOW	Propensity Score Overlap Weight
PARADIGM-HF	Prospective Comparison of ARNI with ACEI to Determine Impact on Global Mortality and Morbidity in Heart Failure
PASS	Post-Authorization Safety Study
PI	Principal Investigator
PPV	Positive predictive value
PRAC	Pharmacovigilance Risk Assessment Committee
PS	Propensity Score
PY	Patient-Year
R	R programming language
RAAS	Renin-Angiotensin-Aldosterone System
RCT	Randomized Controlled Trial
RMP	Risk Management Plan
RR	Relative Risk
SAP	Statistical Analysis Plan
SAS	Statistical Analysis Software package from SAS Institute Inc.
SD	Standard Deviation

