#### 7.3.2.1 Angioedema

Angioedema is characterized by non-pitting edema of the dermis and subcutaneous layers. The most common sites of involvement are the tongue, lips, face, and throat; however, swelling can also occur in the extremities, genitalia, and viscera. Life-threatening airway swelling can also occur ([Lewis 2013](#)).

For angioedema, case validation of a random sample will be performed across databases (where possible) to assess the positive predictive value (PPV) of the identification algorithms. If the PPV is below 80% we will aim to validate all cases if that is feasible and informative.

Two definitions will be used:

*Narrow*: angioedema events identified through disease codes [ICD-9/-10 CM, ICD-10 GM, ICPC, Read] specific for angioedema

*Hypersensitivity reaction*: including symptoms not necessarily specific to angioedema but indicative of potential angioedema events

Code lists and identification algorithms (e.g., with confirmatory treatments such as corticosteroids, epinephrine, or antihistamines) were created in close collaboration with the data partners and will be described in the statistical analysis plan (SAP).

For individual terms planned to identify cases with angioedema, see Annex 3 Section 12.3.1 [Table 12-1](#).

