### **7.5 Study size/power calculation**

[figure not shown]
Since the primary objective of the study is to estimate the IR of angioedema and other safety events of interest with sacubitril/valsartan, [Figure 7-3](#) presents CIs expected for angioedema, the rarest of all the events, given different sample sizes. An IR of angioedema following sacubitril/valsartan was set to be 5.5/1,000 PYs, based on an IR of 2.9/1,000 PYs following

ACEI estimated via meta-analysis, using data up to 1 year from three observational retrospective cohort studies (Figure 7-5 and Table 7-9, random effect Poisson model using data from Burkhart et al 1996, Miller et al 2008, and Toh et al 2012) and set to an IR ratio sacubitril/valsartan/ACEI of 1.9, based on the results of the double-blind part of the pivotal phase III study PARADIGM (McMurray et al 2014). Figure 7-4 shows expected CIs for the hazard ratio (HR) of sacubitril/valsartan versus ACEI for angioedema (exploratory objective [see Section 6.3]) for different sample sizes. In addition to previous assumptions on sacubitril/valsartan and ACEI IRs, the same exposure for sacubitril/valsartan and ACEIs was added.

[figure not shown]
With these assumptions, it is aimed to approximately have 24,000 PY of exposure with sacubitril/valsartan, which will provide an estimated IR of 5.5/1000 PY [95% CI: 4.6-6.5], if we observe 132 angioedema cases.

**Figure 7-3**      **Examples of confidence intervals for the incidence rate of angioedema after exposure to sacubitril/valsartan**

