## 12.3 Annex 3 – Additional information

### 12.3.1 Terms to be used for mapping of outcomes

**Table 12-1 Terms to be used to identify cases with the outcomes of interest**

Outcome of interest	Terms to be used	Comments
Angioedema	ICD-9/-10CM/ICD-10GM/Read/ICPC codes corresponding to angioedema, angioneurotic edema, Quincke edema, or any other synonym Allergic oedema, Anaphylactic reaction, Anaphylactic shock, Anaphylactoid reaction, Anaphylactoid shock, Angioedema, Bronchial oedema, Circumoral oedema, Endotracheal intubation, Epiglottic oedema, Gastrointestinal oedema, Genital swelling, Gleich's syndrome, Intestinal angioedema, Laryngeal dyspnoea, Laryngeal obstruction, Laryngospasm, Laryngotracheal oedema, Genital oedema, Mouth oedema, Oropharyngeal spasm, Palatal oedema, Penile oedema, Penile oedema, Periorbital oedema, Pharyngeal oedema, Reversible airway obstruction, Scrotal oedema, Scrotal swelling, Skin oedema, Swelling face, Swollen tongue, Tongue oedema, Tracheal obstruction, Tracheal oedema, Upper airway obstruction, Vaginal oedema, Visceral oedema, Vulval oedema, Vulvovaginal swelling	Primary analysis (' narrow ' definition)  Sensitivity analysis including additional terms on top of the above (' broad ' definition)  Specifically excluded [because too unspecific, risk of too many false positives]: Endotracheal intubation, Reversible airway obstruction, Skin oedema, Upper airway obstruction  'Endotracheal intubation' to be used however, in the context of assessing severity of angioedema (if available/feasible)
Hypotension	Hypotension, Blood pressure decreased, Orthostatic hypotension, Dizziness, Postural dizziness, Presyncope, Syncope	Specifically excluded [because too unspecific, risk of too many false positives]: Depressed level of consciousness, Loss of consciousness  No BP measurements to be included to identify cases of hypotension  Sensitivity analysis for syncope (as a proxy for severe hypotension)
Hyperkalemia	Hyperkalemia, Blood potassium increased	Include lab values for potassium measurements; definition: K + >5.4 nmol/l
Hepatotoxicity	Acute hepatic failure, Drug-induced liver injury, Hepatic failure, Hepatic necrosis, Acute hepatitis, Fulminant hepatitis, Toxic hepatitis, Hepatocellular injury, Hepatorenal failure, Hepatotoxicity, Liver injury, Hepatic encephalopathy	--

---

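### The planned false negative rate is the PPV of the hypersensitivity definition, so it does not by itself measure the share of angioedema missed by the narrow codes

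*Protocol*

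**What the plan says.** Protocol section 7.7.1.2.3 (Sensitivity analyses) describes the ongoing validation study and states that "the proportion of true angioedema cases among the hypersensitivity reactions is calculated as the false negative rate (FNR". It then gives the purpose: "The FNR will be used to estimate what proportion of angioedema events might have been missed with the narrow definition of angioedema". The list of abbreviations expands FNR only as "False negative rate", and no other section gives a formula.

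Section 7.3.2.1 sets out the two definitions. Narrow means "angioedema events identified through disease codes [ICD-9/-10 CM, ICD-10 GM, ICPC, Read] specific for angioedema". The hypersensitivity reaction definition is described as "including symptoms not necessarily specific to angioedema but indicative of potential angioedema events". The same section plans validation of a random sample of angioedema cases to obtain the PPV of the identification algorithms, and adds: "If the PPV is below 80% we will aim to validate all cases if that is feasible and informative".

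Table 12-1 describes the wider set differently, as a "Sensitivity analysis including additional terms on top of the above", that is, the narrow terms plus others.

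**The concern.** The two sentences in section 7.7.1.2.3 describe quantities with different denominators. The first divides true cases by records flagged by the hypersensitivity definition. The second asks what fraction of all true angioedema events the narrow codes failed to find, so its denominator must be true events.

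The first ratio is the PPV of the hypersensitivity definition. If narrow-coded patients are excluded from the reviewed set, it is also the false omission rate within that set. In neither case is it a false negative rate. It carries no information on how many hypersensitivity records exist, or on how many true cases the narrow codes captured. The missed share depends on both.

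Angioedema is the primary event, and the comparative analyses in section 7.7.1.2.2 use its narrow definition. PPV validation of the narrow codes addresses over-counting. The so-called FNR is the only planned estimate of the share those codes miss.

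**Working it through.** The protocol states no numerical FNR, so there is no figure to reproduce. The check is one of definition, followed by an illustration of size.

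**Notation**
- Nn, PPVn: number of narrow records and their PPV.
- Nh: number of hypersensitivity-only records (no narrow code).
- q: true cases among hypersensitivity-only records divided by Nh. This is the protocol's FNR, and equals PPVh.
- R = Nh/Nn.

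**Formulae**
- Missed true cases: FN = Nh × q = R × q × Nn.
- True cases captured by narrow codes: TP = Nn × PPVn.
- Missed share = FN/(FN + TP) = R × q/(R × q + PPVn).
- Setting this equal to q gives R = PPVn/(1 − q). Only at that value of R does the planned ratio equal the missed share. For smaller R the planned ratio is too high; for larger R it is too low.

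**Inputs**
- Nn = 132, from section 7.5 ("if we observe 132 angioedema cases" in 24,000 PY), used only for scale. The missed share depends on R, q and PPVn, not on Nn. The anchor reproduces: 132/24,000 = 5.5 per 1,000 PY, exact Poisson 95% CI 4.60 to 6.52, matching the stated 4.6 to 6.5.
- PPVn is not given. Assumed 80% (the protocol's threshold for validating all cases) and 100%.
- q and R are not given. Assumed q = 10%, with R from 0.5 to 20.

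**Worked example, q = 10%, PPVn = 80%**
- TP = 132 × 0.8 = 105.6.
- R = 0.5: Nh = 66, FN = 6.6, share = 6.6/112.2 = 5.9%.
- R = 5: Nh = 660, FN = 66, share = 66/171.6 = 38.5%.

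| R | Planned ratio | Missed share, PPVn 80% | Missed share, PPVn 100% |
|---|---|---|---|
| 0.5 | 10% | 5.9% | 4.8% |
| 1 | 10% | 11.1% | 9.1% |
| 5 | 10% | 38.5% | 33.3% |
| 10 | 10% | 55.6% | 50.0% |
| 20 | 10% | 71.4% | 66.7% |

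The planned ratio stays at 10% throughout. The crossing point is R = 0.8/0.9 = 0.89 for PPVn = 80% and 1/0.9 = 1.11 for PPVn = 100%.

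**Effect on a corrected rate, PPVn = 80%**
- Validated narrow rate: 105.6/24,000 = 4.40 per 1,000 PY.
- Including missed cases: 112.2/24,000 = 4.68 at R = 0.5, and 171.6/24,000 = 7.15 at R = 5.

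**Wider range.** For q from 2% to 50%, R from 0.5 to 20 and PPVn from 80% to 100%, the missed share is between 0.40 and 16.7 times the planned ratio.

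**The case against.** The strongest reply is that section 7.7.1.2.3 leaves the details of the sensitivity analyses to the SAP, and says the ratio will be used to estimate the missed proportion, not that it is that proportion. Multiplied by the number of hypersensitivity-only records, it gives the missed cases; with the confirmed narrow cases, it gives the correct share. The ingredients are planned: event rates under both definitions (section 7.7.1.2.2) and the PPV of the algorithms (section 7.3.2.1). This stands in part. A reader might infer that the reported share is bound to be wrong, but a SAP that adds those two steps would get it right. However, the protocol itself fixes a name and a denominator that do not match the stated use, and mentions no further step. The direct reading is the natural one, and on it the result is wrong except at the crossing point.

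Three other inferences are tempting and not supported:
- That this is the plan's only quantitative check on ascertainment. Section 7.6.2 compares incidence from GP data with incidence when secondary care data are added, and benchmarks rates against previous studies. Section 7.7.1.2.2 analyses linked and unlinked subsets separately and estimates rates under both definitions. None of these yields the missed share.
- That narrow cases will be counted as missed, because Table 12-1 builds the wider set on top of the narrow terms. Sections 7.3.2 and 7.3.2.1 list the hypersensitivity definition beside the narrow one, and nothing says that the combined set is the one reviewed. This is an ambiguity of wording.
- That the interim ACEI rate of 1.0 per 1,000 PY (section 5.1), against 1.6 to 4.4 in the cited studies (section 5.1.2), shows missed cases. Section 5.1.2 says that those studies reflect mainly hypertension use. Differences in population, including race, may explain some or all of the gap.

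**Conclusion.** The concern holds. As written, the protocol labels a PPV as a false negative rate and assigns it to a question that it cannot answer alone. In the illustration, a constant reported 10% corresponds to a missed share anywhere from 4.8% to 71.4%. These sizes rest on assumed values of q, R and PPVn; the documents give none of them.

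A reader might infer that the error always gives false reassurance. It does not: the ratio overstates the missed share when hypersensitivity-only records are few. Understatement arises when unspecific records outnumber narrow ones, which is plausible given the long term list in Table 12-1, but the documents give no counts.

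The consequence is confined to the sensitivity analysis of outcome misclassification. The primary incidence rates and the exploratory hazard ratios do not use this quantity and are unchanged.

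**What to change.** In section 7.7.1.2.3, and correspondingly in the SAP:

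1. Rename the planned quantity as the PPV of the hypersensitivity definition.
2. Restrict the reviewed set to patients with a hypersensitivity code and no narrow code, and align section 7.3.2.1 and Table 12-1 with that.
3. Define missed share = Nh × PPVh/(Nn × PPVn + Nh × PPVh), with a confidence interval that carries the sampling error of both PPVs (for example by bootstrap or the delta method). Give it pooled, and by database or cohort where counts allow.
4. Report the corrected rate (Nn × PPVn + Nh × PPVh)/PY beside the narrow rate.
5. State that the missed share is a lower bound, because it counts only missed cases that carry a hypersensitivity code.

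The cost is about one paragraph in each document and a small addition to the programming. The record counts and both PPVs are already to be produced by the planned analyses and the validation study. If the reviewed sample included narrow-coded patients, they need only be separated out, provided that enough hypersensitivity-only records remain.
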